Q2RESEARCH PROTOCOL TEMPLATE INVESTIGATOR INITIATED TREATMENT TRIALS

Title of Project: Treatment of Post-Operative Sinonasal Polyposis with Topical

Furosemide

Principal Investigator: [name], Otolaryngology

Co-Investigators: [name] MD, Otolaryngology; [name],

Otolaryngology; [name], Otolaryngology; [name] PharmD

Abstract

Prior studies have suggested that topical furosemide may reduce the recurrence of sinonasal polyposis following sinus surgery. This project aims to further investigate that claim through a blinded randomized controlled clinical trial following patients who undergo functional sinus surgery for chronic rhinosinusitis with sinonasal polyposis (CRSwP) by randomly assigning participants to receive topical furosemide versus placebo nasal irrigation for 6 weeks post operatively. Outcomes would be compared at 6 months through endoscopic grading scores using Lund Kennedy and Meltzer scores as well as Sino-Nasal Outcome Test (SNOT-22) scores to measure the rate and degree of recurrence and impact on symptoms in the treatment group versus placebo.

A. Specific Aims

State the hypothesis and specific aims. List the long-term objectives and what the proposed research will accomplish.

Hypothesis: Topical furosemide prevents the recurrence of sinonasal polyposis following endoscopic sinus surgery in CRSwP patients

Through investigating this hypothesis, the group aims to provide evidence for treating CRSwP patients with a safe and effective medical therapy to prevent or reduce the recurrence of sinonasal polyposis after sinus surgery. If proven effective in the immediate post operative period, the research would lead to further research aimed at the long term effects of therapy in CRSwP patients to develop a protocol to prevent the recurrence of sinonasal polyps and potentially change the post-operative management of CRSwP patients.

B. Background and Significance

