Performing nasal atomization with 150 mcg twice daily would results in a total exposure of 300 mcg of furosemide daily. Following intranasal administration, a drug may enter systemic circulation through direct local absorption in the nasal mucosa or oral absorption of the swallowed medication¹². When administering intravenous furosemide it has a threshold dose. No diuretic effect is evident at any dose lower than the threshold dose. The threshold dose for intravenous furosemide is 10 mg in a population with normal renal function¹³. Extrapolating this data, a 300 mcg exposure of furosemide should not result in diuresis. A portion of the drug may also be cleared from the sinuses into the throat and swallowed, making it available for gastrointestinal absorption. Furosemide oral solution has a bioavailability of 60%, of that from an intravenous injection of furosemide¹⁴. Therefore swallowed medication should not result in therapeutic levels of furosemide.

After obtaining consent, selected patients will be randomized into 2 groups using the balance block randomization method to either treatment group or placebo group and be scheduled for surgery. Balance block randomization involves the preparation of 4 sheets of paper, writing on 2 sheets "F" for "furosemide" and on 2 sheets "P" for "placebo". The paper sheets will be pooled, placed in a container, and randomly drawn 1 at a time without replacement until all sheets were drawn. The paper sheets will then be placed back into the container and the selection process will be repeated until the sample size is reached. The study investigators will be blinded to the selection process and the randomization will be carried out by the clinical research nurse. A total of 100 patients will be enrolled in the study.

Pre-operatively all patients will receive a 5 day course of 40 mg prednisone, at least one week of and intranasal steroid, and saline irrigation. During a preoperative clinical visit, the degree of sinonasal polyposis will be graded through the Lund Kennedy and Meltzer endoscopic scoring system as well as degree of symptoms through SNOT-22 scores. Also, a demonstration and instructional sheet for how to administer the nasal spray will be distributed at this time.

Then, patients will undergo functional endoscopic surgery as scheduled.

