Immediately post-operatively, patients will begin a 6 week course of twice a day nasal spray If assigned to the treatment group they will receive 300 micrograms of furosemide daily. If assigned to the placebo group, they will receive saline. The clinical research nurse will distribute an unmarked bottle of nasal spray to the study patients either in a pre-operative clinical visit or in the recovery room on the day of surgery. Creation of the study drug will be done by AdvancedRx of Plymouth Meeting, Pa. The department research nurse will store and distribute the study drug to the subjects. Post-operatively, patients will also receive a 40mg prednisone taper (40mg for 3 day, 30mg for 3 days, 20 mg for 3 days, 10 mg for 3 days), nasal saline and a 5-day course of omnicef and at least a 6 week course of intranasal corticosteroid spray. Patients will be given a diary to record any doses that were missed.

Patients taking aminoglycosides will be excluded from this trial as furosemide may increase the ototoxic potential of aminoglycosides. Study subjects who require aminoglycoside use during the study treatment period will be instructed to discontinue taking the study drug and will be removed from the study.

Post-operative visits will be scheduled at 1 week, 3 week, 2 month, 4 month and 6 month intervals. The post-operative visits may be scheduled within 4 days of the scheduled interval. Post-operatively, the degree of nasal polyposis will again be graded through the Lund Kennedy and Meltzer endoscopic scoring system as well as degree of symptoms through SNOT-22 scores. These scores will be obtained at the 2, 4 and 6 month visit.

The duration of participation for the study will be 6 months. Early termination criteria are serious adverse reactions, inability to recruit or adequately enroll an adequate number of patients, problems arise in the study medicine's stability or manufacturing and new toxicological findings that affect the benefit-to-risk ratio.

E. Statistical Methods

If not a pilot study, provide biostatistical design, power calculations determining the number of participants , and the proposed analysis. (suggested length: $\frac{1}{2}$ page)

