- 7. Discuss why risks are reasonable in relation to benefits. Given the minimal risks of topical furosemide, close follow up with monitoring and limited length of a 2-month treatment course in a 6 month study with the potential benefit of preventing the recurrence of nasal polyposis in this complicated subset of patients, the risks of the study are reasonable in relation to the benefits. If proven effective, this study may change the post-operative management of nasal polyposis and provide patients a safe and effective medical therapy to prevent and limit the morbidity of the recurrence of nasal polyps in chronic rhinosinusitis patients.

H. Data and Safety Monitoring Plan

All protocols that pose greater than minimal risk must have a Data and Safety Monitoring Plan (see DHSP policy G 616 "Independent Monitoring of Investigator-Initiated Clinical Trials."

- 1. Describe the Data and Safety Monitoring Plan (DSMP)
 - a. reporting mechanisms for adverse events to the IRB, FDA, and NIH. Investigators will follow all guidelines for reporting to IRB.
 - b. adverse event (AE) grading Adverse events will be graded by investigators using the CTCAE v.4.
 - c. plan for unanticipated AE reporting Unanticipated adverse events will be reported to the IRB per the reporting guidelines.
 - d. plan for annual reporting of AEs
 Annual reporting of AEs will be done at the time of continuing review.
 - e. interim efficacy analysis where appropriate If not, just put n/a, no interim efficacy analysis will be done.
- 2. If applicable, describe the Data and Safety Monitoring Board (DSMB) that will be responsible for monitoring the study. Indicate Chair, members, areas of expertise, frequency of meetings, distribution of reports. There is no DSMB for this study.

I. Literature Cited

List only literature cited within the text. (suggested length: no more than 12 references)

Date	5/10/2018
Version	6.0

Research Protocol Template, 11/15/2010

- ⁶ P.S. Batra, L. Tong, M.J. Citardi Analysis of comorbidities and objective parameters in refractory chronic rhinosinusitis Laryngoscope, 123 (Suppl 7) (2013), pp. S1–S11
- ⁷ Wynn, R. and Har-El, G. (2004), Recurrence Rates after Endoscopic Sinus Surgery for Massive Sinus Polyposis. The Laryngoscope, 114: 811–813. doi:10.1097/00005537-200405000-00004

 ⁸ Niven AS, Argyros G (2003) Alternate treatments in asthma. Chest 123(4):1254–1265

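### Randomised patients who need an aminoglycoside during treatment are removed from the study as well as taken off the drug, which on the ordinary reading loses their 6-month outcome

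*Combined protocol and SAP*

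**What the plan says.** Section D (Research Design and Methods) sets the order of events: "After obtaining consent, selected patients will be randomized into 2 groups", then surgery, then study drug. The rule at issue applies to "Study subjects who require aminoglycoside use during the study treatment period", who "will be instructed to discontinue taking the study drug and will be removed from the study".

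On outcome timing, Section D says of the endoscopic and SNOT-22 scores: "These scores will be obtained at the 2, 4 and 6 month visit". On the visit window: "The post-operative visits may be scheduled within 4 days of the scheduled interval". The Abstract gives the time of comparison: "Outcomes would be compared at 6 months through endoscopic grading scores".

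Treatment length is given in two ways. Section D says that "patients will begin a 6 week course of twice a day nasal spray"; Section G, item 7, speaks of the "limited length of a 2-month treatment course in a 6 month study".

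Section E names the t test and Fisher's exact test. It gives no analysis set and no rule for missing outcomes. Section G, item 5, promises follow-up for adverse reactions at all post-operative visits, and for serious effects it mentions intervention or stopping the drug, not leaving the study.

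**The concern.** Stopping a drug and leaving a trial are separate acts, and the sentence joins them. Section D gives a safety reason for stopping (ototoxicity) but none for ending follow-up.

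The trigger is a need for a particular antibiotic after sinus surgery, and the outcomes are endoscopic and symptom scores. A link between the two is plausible. If there is one, the patients left in the comparison are no longer the randomised groups, and the scheduled scores that would show whether this matters will not have been taken. It is also unclear whether the adverse-reaction visits in Section G continue for patients who stopped because of a safety rule.

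**Working it through.** **1. The plan's own figures.** Assume that 30% is recurrence on control and 6% on furosemide; Section E does not label the percentages. For two-sided 5% and 80% power, with mean proportion 0.18:

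- Uncorrected n = [1.96·√(2·0.18·0.82) + 0.842·√(0.21 + 0.0564)]² / 0.24² = 39.03 per arm.
- With continuity correction, n = (39.03/4)·[1 + √(1 + 4/(39.03·0.24))]² = 46.99, so 47. This matches Section E.
- Full enumeration of Fisher's test gives 82.5% power at 47 per arm, so the stated 80% is slightly conservative. For 38% vs 79% at 40 per arm it gives 95.6% (stated 95%).
- 100 patients in blocks of four make 25 blocks, so 50 per arm. Exact power for 30% vs 6% is then 85.7%.

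**2. When removal falls relative to the scores.**

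- A 6-week course ends at day 42.
- The 2-month visit, taken as day 56 to 61, less the 4-day window, is no earlier than day 52 to 57.
- Removal on a 6-week course therefore precedes every post-operative score by at least 10 days.
- On a 2-month course, only removals in about the last 4 days (4/60, about 7%) could follow a 2-month score. The 6-month outcome is lost on either wording.

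**3. What kind of bias is possible.** Suppose that 20% of recurrences are removed in both arms alike (illustrative only: 3 control patients and 0.6 of a furosemide patient on average).

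- Control: 0.24/0.94 = 25.5%. Furosemide: 0.048/0.988 = 4.9%.
- The difference is 20.7 points instead of 24.

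Outcome-related removal can thus bias the estimated difference even when it acts alike in both arms. With no treatment effect, the same removal leaves both arms equal, so a false difference would need removal to act differently by arm.

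**4. How much could be left unknown.** No aminoglycoside rate is given, so the range is assumed. Each missing outcome leaves 1/50 = 2 points of the arm difference unidentified. With 15 and 3 recurrences observed and k outcomes missing per arm, the worst case is 15/50 vs (3+k)/50 and the best case is (15+k)/50 vs 3/50.

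| k per arm | Bounds on difference (points) | Worst-case Fisher p |
|---|---|---|
| 1 | 22 to 26 | 0.009 |
| 2 | 20 to 28 | 0.023 |
| 3 | 18 to 30 | 0.048 |
| 4 | 16 to 32 | 0.090 |

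**5. What retention costs.** Let s furosemide patients stop early and, at the extreme, revert to 30% recurrence. The furosemide count is then Bin(50−s, 0.06) + Bin(s, 0.30). The comparator removes those s patients only (50 vs 50−s).

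| s | Power, retained | Power, removed | Cost vs removal (points) | Fall from 85.7% (points) |
|---|---|---|---|---|
| 1 | 83.5% | 86.2% | 2.7 | 2.2 |
| 2 | 81.2% | 86.8% | 5.5 | 4.5 |
| 3 | 78.8% | 87.3% | 8.5 | 6.9 |

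Power rises slightly on removal because Fisher's test is discrete. For a t-tested score with an assumed 0.566 SD effect (80.0% power at 50 per arm), retention multiplies the effect by (1 − s/50) and gives 78.4%, 76.7% or 75.0%. Removal gives 79.6%, 79.2% or 78.7%. The cost is about 1.2 to 3.8 points.

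For losses unrelated to outcome, exact power is still 80.05% at 44 per arm.

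**The case against.** The strongest reply is that the rule is rare, blind to arm and driven by safety. Current aminoglycoside users are excluded at entry, and the routine post-operative antibiotic, omnicef, is given to everyone and so is evidently outside the rule. The worst-case bound passes p = 0.05 only with four missing per arm, all falling the unfavourable way. This stands, and it is why the point is minor.

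Secondly, the protocol never says in so many words that scores stop. Removal is not defined, and Section G, item 2, lists the medical record and endoscopic findings as data sources, so some endoscopy results might survive there. The consent pages are not in the text available, and they may address contact after removal. This also stands in part: the loss of the outcome is the ordinary reading, not a literal statement. But use of record data after removal is not addressed, and a record would not reliably supply graded endoscopy and SNOT-22 scores at 6 months.

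Thirdly, retention dilutes the effect. That is true. A reader might infer from the t-test figures that the cost is at most about 4 points of power. For recurrence, the type of endpoint on which the sample size rests, it can be larger and can take power below 80%. Those figures assume that every retained patient loses all benefit and that all of them are in the furosemide arm.

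**Conclusion.** The point holds as a cheap improvement: as written, the plan excludes some randomised patients after randomisation when it need not. It rests on the ordinary meaning of removal and on the absence of any provision for later visits.

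Two stronger inferences are not supported:

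- A reader might conclude that the result will be biased. The documents give no aminoglycoside rate and no evidence that such use relates to outcome or differs by arm, so the size of any bias cannot be stated.
- A reader might conclude that the rule endangers power. It does not in any plausible range: a few losses unrelated to outcome leave power above 80%, and retention may itself lower power.

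The benefit is that outcomes exist and can be examined. Severity: minor.

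**What to change.** Leave the drug-stopping instruction unchanged. In Section D, replace the clause on removal with: *and will remain in follow-up, unless consent is withdrawn, with the scheduled 2-, 4- and 6-month scores and adverse-event review*.

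Add to Section E: *All randomised patients with a 6-month outcome are analysed in the arm assigned, whatever treatment was received; missing 6-month outcomes are reported by arm and reason.*

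A best- and worst-case check for recurrence is optional. Shifted multiple imputation is not needed for this point.

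The cost is one clause and one sentence, at visits already scheduled, plus the possible dilution shown above.

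Separately, the 6-week course in Section D and the 2-month course in Section G, item 7, must be reconciled, because they set the window in which the rule applies.

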Describe the research design and procedures to be used (what, when, how) Include the duration of participation and early termination criteria. Provide a flow diagram or timetable. Procedures, situations, or materials that may be hazardous to personnel and the relevant precautions, should be outlined here. (suggested length not more than 2 pages)

Through a blinded randomized controlled clinical trial, the recurrence rates of nasal polyps in patients with chronic rhinosinusitis with polyps who are undergoing sinus surgery will be compared through their response to therapy with topical furosemide versus placebo. Eligible patients will be recruited through the Otolaryngology Department at Thomas Jefferson University Hospital. During pre-operative clinical visits, eligible patients will be selected and provided the option to participate in the study.

Topical sinus medications have been administered via Mucosal Atomization Device (MAD) in the treatment of chronic rhinosinusitis. Kanowitz et al studied the use of budesonide respules administered via MAD in refractory postoperative

rhinosinusitis⁹. A separate study found that medication administered via the MAD resulted in distribution to the maxillary sinus, ethmoid cavity, and frontal recess post endoscopic sinus surgery¹⁰.

When administering furosemide via the MAD, a total daily dose used in a previous nasal spray trial of 300 mcg was utilized¹¹. Patients may administer 75 mcg/0.3 ml to each nostril twice daily to result in the total daily dose of 300 mcg. The volume of 0.3 ml to each nostril is the volume recommended by the manufacturer for intranasal administration via the MAD nasal device.

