Based on prior randomized controlled clinical trials, the study is powered to achieve at least 80% power. Based on the results published by Hashemian et al.¹, Group sample sizes of 40 in ctrl and 40 in treat achieve 95% power to detect a difference of 38% vs. 79% using two-sided Fisher's Exact Test with significance level 5%. Also based on results published by Passali et al.², group sample sizes of 47 in ctrl and 47 in treat achieve 80% power to detect a difference of 30% vs. 6% using two-sided Fisher's Exact Test with significance level 5%.

The primary outcomes will be compared through the independent t test for continuous variables and the Fischer exact test for nominal variables. All statistical analyses will be performed at a significance level of 0.05.

F. Gender/Minority/Pediatric Inclusion for Research

All protocols must include documentation of the inclusion of women and minorities in the research protocol. If women and minorities are not to be included, provide rationale for exclusion.

The study will include women and minorities.

G. Human Subjects

1. Provide number, age range, and health status of the subject population. List criteria for inclusion or exclusion.

100 patients, 18 to 65 years old, chronic rhinosinusitis with sinonasasl polyposis

Inclusion Criteria:

Patients with chronic rhinosinusitis and sinonasal polyposis who are candidates for functional endoscopic sinus surgery

Exclusion Criteria:

Hypersensitivity to furosemide or sulfonamides, pregnancy, history of tinnitus, history of sensorineural hearing loss, poorly controlled diabetes, current diuretic therapy, known electrolyte disorder, currently taking aminoglycosides, BUN and creatinine levels out of the normal range, history of renal disease, allergy to sulfonamides.

2. Identify sources of research material in the form of specimens, records or data.

Patient medical record, physical exam findings (endoscopic scores), SNOT-22 questionnaire,

3. Describe plans for recruitment and consent procedures to be followed.

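### Recurrence is neither named as the single primary outcome nor defined by a score and cut-off, while unlisted primary outcomes are all tested at 0.05; if any one 6-month result may count as success, the false-benefit risk is about 4–7% rather than 2.5%

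*Combined protocol and SAP*

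**What the plan says.** Section A (Specific Aims) gives one hypothesis: "Topical furosemide prevents the recurrence of sinonasal polyposis following endoscopic sinus surgery in CRSwP patients". Section D (Research Design and Methods) says that "the recurrence rates of nasal polyps in patients with chronic rhinosinusitis with polyps who are undergoing sinus surgery will be compared" between furosemide and placebo. Section E (Statistical Methods) sizes the trial with two comparisons of proportions by two-sided Fisher's exact test at 5%: 38% vs 79% with 40 per arm for 95% power, and 30% vs 6% with 47 per arm for 80% power.

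The measurements are scores. The Abstract states "Outcomes would be compared at 6 months through endoscopic grading scores using Lund Kennedy and Meltzer scores", together with SNOT-22, "to measure the rate and degree of recurrence and impact on symptoms in the treatment group versus placebo". In Section D, after surgery "the degree of nasal polyposis will again be graded through the Lund Kennedy and Meltzer endoscopic scoring system", with SNOT-22 alongside, and "These scores will be obtained at the 2, 4 and 6 month visit".

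The analysis rule in Section E is "The primary outcomes will be compared through the independent t test for continuous variables and the Fischer exact test for nominal variables". It is followed by "All statistical analyses will be performed at a significance level of 0.05".

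**The concern.** Three things are missing together.

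- **No named primary outcome.** Section E speaks of primary outcomes in the plural and lists none. It assigns tests by type of variable. Because a t test is included, continuous scores are apparently among them, although the sample size concerns only a yes/no event.
- **No definition of the event.** Two endoscopic gradings are recorded at three visits. Nothing says which grading decides recurrence, or at what value.
- **No error control.** There is no order, adjustment or success rule for the several tests at 0.05.

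If this stands, the event that justifies the sample size can be chosen after the scores are known. One significant score among several could also carry the primary claim. The stated 80% and 95% power cannot be tied to the analysis that will actually be run.

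**Working it through.** **Inputs from the documents.** 100 patients in blocks of four with two per arm (Section D), so 50 per arm. Two-sided 0.05, which is 0.025 in the direction of benefit. Three scores at 6 months: Lund Kennedy, Meltzer and SNOT-22. Planning rates as in Section E.

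**Assumptions, not in the documents.** Equal correlation of 0.5, 0.7 or 0.9 between scores; any one p < 0.05 counts as success; recurrence rates without effect of 18%, 30% or 38%; three candidate cut-offs per score; 10% loss.

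**1. The plan's own sample sizes.** The formula for two proportions is n = [1.96·√(2·p̄·(1−p̄)) + z·√(p₁(1−p₁) + p₂(1−p₂))]² / d², where z belongs to the power and d is the difference. The continuity correction is n′ = (n/4)·[1 + √(1 + 4/(n·d))]².

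- 30% vs 6%, 80% power: n = (1.065 + 0.434)²/0.24² = 39.0; n′ = 47.
- 38% vs 79%, 95% power: n = (1.366 + 1.042)²/0.41² = 34.5; n′ = 40 (39.2 rounded up).

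Both match Section E. Full enumeration of Fisher's test gives power of 82.5% at 47 per arm and 95.6% at 40 per arm. The sample-size arithmetic is sound.

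**2. Do the planning rates identify the event?** Read in the stated order of control then treatment, the first pair rises by 79 − 38 = 41 points and the second falls by 30 − 6 = 24. Either the two pairs count different events or the arms are listed in different orders. Section E does not say which.

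**3. Any one result counts, no true effect.** For k equally correlated test statistics, P(at least one false benefit) = 1 − ∫ φ(u)·Φ[(1.96 − √ρ·u)/√(1−ρ)]ᵏ du. With three independent tests this is 1 − 0.975³ = 7.3%, an unlikely upper bound. The last two rows of the table, and both either-direction rows, come from 40,000 simulated trials per setting with t tests. Where recurrence is added, it is one score cut into yes/no and tested by Fisher, averaged over the three assumed null rates.

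| Correlation | 0.5 | 0.7 | 0.9 | Single test |
|---|---|---|---|---|
| Three scores, benefit | 6.3% | 5.5% | 4.2% | 2.5% |
| Three scores, either direction | 12.7% | 11.1% | 8.4% | 5% |
| Scores plus recurrence, benefit | 7.1% | 6.2% | 4.9% | 2.5% |
| Scores plus recurrence, either direction | 14.1% | 12.4% | 9.7% | 5% |

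A separate simulation of 20,000 trials per setting, with cut-offs at 30% and 50%, gives 4.7–7.0% for benefit with recurrence included.

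**4. Recurrence is the only primary outcome, but its definition is picked after the results.** By enumeration at 50 per arm, Fisher's two-sided size is 2.7% (null rate 18%) to 3.1% (30% and 38%), half of it in each direction: 1.3–1.6% for one fixed definition.

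- Best of three cut-offs on one score: 3.2–3.3% false benefit.
- Best of two scores with three cut-offs each: 6.1%, 5.8% and 5.2% at correlation 0.5, 0.7 and 0.9.

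**5. Power of one Fisher test, by enumeration.**

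| Rates | 50 per arm | 45 per arm (10% loss) |
|---|---|---|
| 38% vs 79% | 98.6% | 97.3% |
| 30% vs 6% | 85.7% | 81.2% |
| 25% vs 5% (same 5:1 ratio, assumed) | 74.8% | – |
| 20% vs 4% (same 5:1 ratio, assumed) | 59.4% | – |
| 40% vs 16% (same 24-point gap, assumed) | 71.3% | – |

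The definition determines the rates, so it also determines the power.

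**The case against.** Recurrence is clearly the intended outcome: it is the only hypothesis, the stated design comparison and the only thing powered, and the Abstract places the comparison at 6 months. That reading is fair. It still leaves the score and cut-off open, and it does not account for a t test applied to primary outcomes.

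The 4–7% depends on a success rule that the plan does not state and on assumed correlations. That is true, so the figure is conditional. The plan does not exclude the rule either, and the missing definition needs no assumption.

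The figures for a definition picked late use cut-offs and null rates chosen for illustration, and they are set against Fisher's actual size rather than 2.5%. This also stands. Against 2.5%, three cut-offs on one score add less than one point; a choice across both scores still gives about twice 2.5%.

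The order of the percentages does not change the sample size. With equal arms, two-sided Fisher power is the same if the arms are swapped or the complementary event is counted. So the unclear order leaves the event unidentified, but it does not show that 40 or 47 per arm is wrong. The lower power figures rest on hypothetical rates and show sensitivity only.

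Finally, several primary outcomes with Holm's adjustment or a fixed testing order would also control the error and keep symptoms in the primary claim. That is statistically valid, but recurrence would still need a definition, and power would have to be shown for the adjusted tests.

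**Conclusion.** The point holds and should be fixed before any outcome data are reviewed. That no outcome is named primary, no recurrence definition is given and no multiplicity rule is stated follows from the text alone.

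The size is conditional. If any one 6-month result may count as success, false benefit is about 4–7% instead of 2.5% at correlation 0.9 to 0.5. If recurrence is the sole primary outcome but is defined late across both endoscopic scores, it is 5.2–6.1%. Limiting the count to 6 months is the cautious reading: nine tests (three scores at three visits, equally correlated) would give 6.2–13.5%.

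The planned 50 per arm is adequate for one Fisher test, but only if the chosen definition yields rates like those used for planning.

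**What to change.** In Section E, state that the single primary outcome is polyp recurrence at 6 months, one value per patient, derived from one named endoscopic score already collected and a stated cut-off, and tested once by two-sided Fisher's exact test at 0.05. The sponsor chooses the score and cut-off and writes them into the protocol before looking at any outcome data, pooled data included.

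In the power paragraph, give the arm and the event for each percentage. Confirm that the chosen definition counts that event, or recompute power for the rates it is expected to give.

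Label the 6-month Lund Kennedy, Meltzer and SNOT-22 comparisons as secondary; ordered testing or Holm among them is optional. Align the outcome list in the Abstract.

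The cost is wording. No visit or measurement is added, and no patients are added provided the definition yields the planning rates. The price is that a score result alone can no longer carry the primary claim.

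### The 6-month t test and Fisher test make no use of the 2- and 4-month scores, so a patient without a 6-month score adds nothing, and loss linked to earlier scores can bias the estimate

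*Combined protocol and SAP*

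**What the plan says.** The Abstract fixes the time point: "Outcomes would be compared at 6 months through endoscopic grading scores using Lund Kennedy and Meltzer scores", together with SNOT-22. Section D has the scores taken once before surgery and again afterwards: "These scores will be obtained at the 2, 4 and 6 month visit". Section E then names the tests: "The primary outcomes will be compared through the independent t test for continuous variables and the Fischer exact test for nominal variables", at a significance level of 0.05. It also states that "the study is powered to achieve at least 80% power", and supports this with two pairs of rates from earlier trials: 38% vs 79% with 40 per arm, and 30% vs 6% with 47 per arm. Section D sets enrolment at 100.

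The documents contain no missing-data rule, no analysis population, no dropout assumption and no role for the 2- and 4-month scores in the comparison. Recurrence is not defined. Section D removes patients who come to need aminoglycosides during treatment, without saying how they are analysed.

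**The concern.** A two-sample test on a 6-month value can use only patients who have that value, and nothing in the plan supplies one for the rest. A patient scored at 2 and 4 months but not at 6 therefore leaves the comparison, although the earlier scores carry information about the missing one. Study treatment lasts 6 weeks, so more than four months are follow-up only, and some loss is foreseeable. Patients whose polyps return, or who feel well, may be the ones who stop attending.

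If loss is unrelated to the scores, only power is lost. If it depends on the earlier scores and the treatment has an effect, the 6-month difference is also biased. Adjusting for the pre-operative score among completers does not repair this, because the same patients are still left out.

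**Working it through.** **Inputs from the documents.** 100 enrolled, 1:1, so 50 per arm; two-sided Fisher test at 5%; 30% vs 6% and 38% vs 79%; scores before surgery and at 2, 4 and 6 months. **Assumed.** All loss rates, the 0.6 SD effect and the correlations between visits.

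**1. The plan's own figures.** Exact Fisher power by full enumeration is 95.6% at 40 per arm for 38% vs 79% (stated: 95%) and 82.5% at 47 per arm for 30% vs 6% (stated: 80%). The continuity-corrected formula gives 40 and 47 per arm, so the stated sample sizes reproduce.

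**2. Margin for loss.** 100 - 2 × 47 = 6 patients, or 6%. With random loss, exact power for 30% vs 6% is 85.7% at 50 per arm, 81.2% at 45 (10% loss), 80.1% at 44 (12%) and 79.5% at 42 (16%).

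**3. Binary outcome, loss linked to recurrence, same pattern in both arms.** Let l1 be the loss among recurrent patients and l0 among the others. The observed rate is p(1 - l1) / [p(1 - l1) + (1 - p)(1 - l0)], and completers are 50 times the denominator. For 30% vs 6% the mean rate is 18%. With 15% overall loss and l1 = 3 × l0:

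- l0 = 0.15 / (3 × 0.18 + 0.82) = 0.110 and l1 = 0.331.
- Control: 0.30 × 0.669 = 0.201; 0.70 × 0.890 = 0.623; rate 0.201 / 0.824 = 24.4%; 41 completers.
- Treated: 0.06 × 0.669 = 0.040; 0.94 × 0.890 = 0.836; rate 0.040 / 0.877 = 4.6%; 44 completers.

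The other rows follow in the same way. Differences are taken from unrounded rates.

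| True rates (control vs treated) | Overall loss | Who leaves 3:1 | Observed rates | Difference in points (true) | Fisher power |
|---|---|---|---|---|---|
| 30% vs 6% | 0% | - | 30% vs 6% | 24.0 (24.0) | 85.7% |
| 30% vs 6% | 10% | recurrent | 26.5% vs 5.1% | 21.4 (24.0) | 82.3% |
| 30% vs 6% | 15% | recurrent | 24.4% vs 4.6% | 19.8 (24.0) | 74.3% |
| 30% vs 6% | 15% | well | 32.8% vs 6.8% | 26.0 (24.0) | 83.5% |
| 79% vs 38% | 15% | recurrent | 76.2% vs 34.3% | 41.9 (41.0) | 97% |
| 79% vs 38% | 15% | well | 82.1% vs 42.7% | 39.3 (41.0) | 97% |

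The last two rows read the first cited pair as recurrence rates. Section E does not say which outcome the percentages count. Read as relapse-free rates (recurrence 62% vs 21%), the two differences change places and power is again about 97%.

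**4. No true effect.** At 30% in both arms, 15% loss and a 3:1 pattern in both arms, both observed rates are 25.4% and the rejection rate is about 3.0%. A pattern that differs by arm is another matter. With 10% loss except for 40% of recurrent patients in one arm, the observed rates are 30.0% vs 22.2% (45 and 40 completers) and the rejection rate is about 9.9%.

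**5. What the interim status recovers.** In a simulation of 30% vs 6% with 50 per arm, 36% of patients with polyps at month 4 were lost against 11% of the others. The complete-case difference averaged 20.5 points. Standardising over month-4 status (within each arm, the sum over status of the share with that status times the 6-month rate among those observed) gave 24.1, against a true 24. In step 3 loss depends on 6-month recurrence itself, so month-4 status would help there only as far as it predicts that outcome.

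**6. Continuous scores.** Simulation with 50 per arm, true effect 0.6 SD, visit correlations 0.55-0.7 and about 15% loss rising with the month-4 score:

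- 6-month t test: 0.54-0.57 SD, that is (0.60 - 0.57) / 0.60 = 5% to (0.60 - 0.54) / 0.60 = 10% too small; power about 71-75%.
- Completers adjusted for the pre-operative score: 0.54-0.58 SD.
- Estimate using the 2- and 4-month scores: 0.60 SD.

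With random loss to 42 per arm, t-test power is about 78% (0.6 × √(42/2) = 2.75, against a critical value of 1.99).

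**The case against.** Section E names tests, not an analysis set. A reader might infer that the plan lays down the exclusion of patients without a 6-month score. It does not; the exclusion follows from the tests, the time point and the absence of any other rule. If recurrence meant recurrence at any visit, events seen at 2 or 4 months would still count in the Fisher test and most of the binary bias would go. The Abstract's 6-month comparison points the other way, and the comparison of scores is affected under either reading.

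A reader might also infer that early recurrence among those lost always shrinks the effect, or that power always falls below target. Neither holds. The direction reverses between plausible readings of the plan's own rates, and power for 30% vs 6% stays above 80% with 10% loss at 3:1, or with 15% loss when well patients leave more often.

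Nor do the documents support reading the planned tests as invalid. With the same loss pattern in both arms they hold their level under no effect. Excess false positives need a pattern that differs by arm, and nothing in the documents shows that one is expected.

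The objection also limits the remedy. Imputing recurrence separately by arm would be unstable: 6% of 50 is about 3 expected treated events, and with 42 completers the chance of at most one is 27%. Fisher p-values have no standard rule for pooling across imputations.

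What stands is that the plan collects the interim scores, does not use them in the comparison and has no rule for a missing 6-month value.

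**Conclusion.** The point holds as a cheap improvement to the analysis, not as a fatal flaw. Under the assumed 15% loss driven by the month-4 score, the t test understates a 0.6 SD effect by about 5-10%, with power of 71-75%, and using the interim scores removes essentially all of that bias. For recurrence at 30% vs 6%, the pair that sets the sample size, power at about 15% loss is 74% if recurrent patients are three times as likely to be lost, 79.5% if loss is random (42 per arm) and about 83% if well patients are the ones lost. For 38% vs 79% it is about 97% throughout. The loss rates, the SD-scale effect and the correlations are all assumptions, so these figures show a plausible range and do not predict what this trial will see. Bias in the estimate requires loss related to the scores together with a true effect, or a loss pattern that differs by arm.

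**What to change.** In Section E:

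- **Endoscopic scores and SNOT-22.** Replace the 6-month t test with a mixed model for repeated measures on the 2-, 4- and 6-month scores, in all randomised patients with any post-operative score. Include arm by visit, pre-operative score by visit and an unstructured covariance. Take the 6-month arm difference as the estimate, and keep the complete-case t test as a sensitivity analysis.
- **6-month recurrence.** Define it. Keep Fisher's test on observed cases and add an estimate that uses month-4 (or last observed) polyp status. This can be standardisation over that status, or multiple imputation from one parsimonious model pooled over both arms (arm plus latest endoscopic score, penalised if events are sparse). Combine the risk difference, not Fisher p-values, by Rubin's rules.

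The cost is a few lines of text and slightly more analysis, with no new visits, data or patients. The added analyses rely on loss being explained by the observed scores. Patients lost before month 2 gain nothing beyond their pre-operative score. The choice should be fixed before outcome data are seen.
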